**Table 9.3.2.2:1 Treatment management variables at time of enrolment**

Variables	Obtained from patient medical records	Obtained at the study visit by direct interview with the patient
In case of previous treatment with VKA: treatment duration (start and stop date if available) and reasons for VKA treatment switch	X *	
First NOAC initiated (active substance, dose, start date, end date)	X *	
History of thromboembolic and bleeding events	X	X (if applicable)
History of NOAC treatments prior to current NOAC (if applies):  - Dose changes: start date – end date, new dose, and reason  - NOAC switch: start date – end date, dose and/or dose changes and reason	X	X (if applicable)
Frequency of visits to the physician: "How many times a year do you visit the cardiologist?"		X

\* Already obtained for primary objective.

### **9.3.3 Covariates**

**Table 9.3.3: 1 Covariates: Baseline variables at time of first NOAC initiation**

Variables	Obtained from patient medical records
Demographic characteristics (gender, work status, life status)	X
Alcohol consumption	X
Physical activity	X
Systolic BP/Diastolic BP	X
AF diagnosis date	X
In case of previous treatment with VKA: treatment duration (start and stop date if available) and reasons for VKA treatment switch	X
First NOAC initiated (active substance, dose, start date, end date)	X
Kidney function (serum creatinine (mg/dl), creatinine clearance (CG equation) obtained from medical charts or auto-calculated)	X
Liver function (AST/ALT, total bilirubin)	X
Concomitant and relevant previous diseases (Ischaemic stroke or TIA, Systemic embolism, Heart Failure, Coronary artery disease, Ischemic cardiomyopathy, Left ventricular dysfunction, Cerebrovascular disease, Renal disease, Liver disease, Bleeding, Hypertension, Diabetes mellitus, Hyperlipidemia, COPD, Gastric and duodenal ulcers, Dementia, Anemia, Rheumatic disease, Cancer, Prosthetic heart valves, Others)	X
Concomitant treatments (ARB or ACE inhibitor, Beta-blocker, Calcium channel blockers, Diuretics, Amiodarone, Statin, Proton-pump inhibitor, H2-receptor antagonist, Aspirin, Other Antiplatelet agents, Digoxin, NSAIDs, Verapamil / Dronedarone, Other antiarrhythmics, ketoconazol (systemic), ciclosporine, itraconazol, Others)	X

### **9.4 DATA SOURCES**

Data collection will be limited to those available in the medical records of selected patients.

Variables collected at time of first NOAC initiation (see Table 9.3.2.1: 1 and Table 9.3.3 :1 ) will be obtained based on patient's medical records.

Patient knowledge about his condition and other variables collected at time of patient enrolment (new data, see Table [9.3.2.2: 1](#)) will be obtained by interviewing the patient.

## **9.5 STUDY SIZE**

It is planned that a total of approximately 1000 patients will be recruited for the study. Based on such sample size estimates, categorical variables of binomial proportions (e.g. gender) will be estimated with the precision (i.e. width of descriptive 95% confidence interval) described in the table [9.5: 1](#).

**Table 9.5: 1 Width of 95% confidence interval by precision**

Prevalence of attribute	Sample size
	1000
10% Expected n	100
95% CI width	3.73
20% Expected n	200
95% CI width	4.95
30% Expected n	300
95% CI width	5.67
40% Expected n	400
95% CI width	6.06
50% Expected n	500
95% CI width	6.18

## **9.6 DATA MANAGEMENT**

The data will be entered by the investigators themselves and/or authorized personnel directly in the electronic case report form (eCRF). A data management plan (DMP) will be created to describe all functions, processes, and specifications for data collection, cleaning and validation. The eCRFs will include programmable edits to obtain immediate feedback if data are missing, out of range, illogical or potentially erroneous.

AE reconciliation will be performed quarterly from study initiation date.

When data management is outsourced, the designated contract organization will be responsible for the development and implementation of the data management plan and preparation of the data handling report according to the sponsor's standards.

The database will be housed in a physically and logically secure computer system maintained in accordance with a written security policy. The system will meet the standards of the International Committee on Harmonization guideline E6R1 regarding electronic study data handling. Patient confidentiality will be strictly maintained.

## **9.7 DATA ANALYSIS**

Analyses will be performed by Boehringer Ingelheim's designees. The analysis population will consist of all eligible patients (i.e. all patients fulfilling all inclusion criteria and no exclusion criteria). If patients have missing values for an outcome, those patients will be excluded for that outcome's analysis.

In this non-interventional study, retrospective data from medical charts and data at the study visit will be collected for non-valvular AF patients. Once the study has been completed and all data from the last patient have been recorded, the database will be closed and statistical analysis will be performed.

The proposed methods for statistical analysis presented below are a summary of the methods that will be applied in the study to analyse the data collected and to answer the study objectives.

Since the study is descriptive the variables included in the study objectives will be summarized overall and by factors of interest. All results will be summarized with measures of central tendency (mean and median), variability/dispersion (standard deviation and interquartile ranges), absolute and relative frequencies, and ranges.

A Statistical and Epidemiological Analysis Plan (SEAP), will be prepared to describe all processes, treatment and specifications for and the planned statistical analysis.

### **9.7.1 Main analysis**

The primary outcome is the usage of NOACs in patients with NVAF, based on the baseline characteristics at the time of first NOAC initiation. Baseline (at time of first NOAC initiation) variables will be analyzed descriptively by NOAC type. Standardized differences between Dabigatran Etexilate and each of the other NOACs separately will be estimated for these variables.

For the secondary outcomes, the following analyses are planned:

Appropriateness of NOACs prescription based on national recommendations (positioning therapeutic report) (11) is planned to be done for the entire eligible patients.

For NOAC treatment management, descriptive analysis of history of thromboembolic and bleeding events, frequency of visits to the physician, first NOAC (start - end date, dose), dose change/adjustment (start date - end date, new dose, reason for change) and new NOAC initiation (start - end date, new treatment, new dose, reason for change) will be done. Prior VKA use and reasons for switch (already collected as a baseline variable) will be also considered for this outcome.

Variables regarding patient knowledge collected at time of patient enrolment will be analysed descriptively (independent of NOAC type). Each question will be analyzed separately.

## **9.8            QUALITY CONTROL**

The eCRF will include programmable edit checks to obtain feedback if data is missing, out of range, illogical or potentially erroneous. These checks will be performed once data is entered into the eCRF. Thus the data entered in to the eCRF will be validated within the system and the physician will receive alerts for missing or inconsistent data. In case any changes of already entered data will be required, an audit trail will be available.

No regular source data verification is planned in this study. However, in case of decreasing compliance (i.e. of missing data, data discrepancies, protocol violations, etc.) a for-cause audit or risk-based monitoring visit could be performed.

Strict and continuous quality control will be maintained to ensure the accuracy and scientific rigor of the data obtained, maintaining uniform conditions for collecting the information. Quality control will be carried out by qualified personnel designated for this purpose.

A quality assurance audit/inspection of this study may be conducted by the sponsor or sponsor's designees or by Independent Ethics Committee (IECs) or by regulatory authorities. The quality assurance auditor will have access to all medical records, the investigator's study-related files and correspondence, and the informed consent document of this study.

## **9.9 LIMITATIONS OF THE RESEARCH METHODS**

A NIS is the most suitable design to obtain information about the use of medicines in everyday therapeutic practice and thus for investigating questions in everyday therapeutic practice. However, there are some limitations inherent to this design.

Consecutive enrolment will be employed to minimize selection bias. The entry criteria are less restrictive than the ones of a randomized clinical trial, which will permit the enrolment of a broader patient population.

The choice of NOAC was done before the study visit and it is done at the discretion of the investigator. However, as the setting is limited to the hospital setting (Cardiology Services), patients treated in other clinical settings will not be part of this study. Patients seen by their physician less than twice per year are therefore less likely to be included in the study. Patients with higher frequency of visits are more likely to be included in the study and could be over-represented in the sample. Additionally, having 10 patients recruited in each site, patients from the larger practice hospitals will also be under-represented.

As patients are included after first NOAC initiation and need to be treated by a NOAC at time of enrolment, any patient having prematurely discontinued any NOAC treatment between the time of first NOAC initiation and the start of the enrolment period will not be included in the study. The sample may therefore not be representative of all patients having initiated a NOAC since November 2016.

Channeling bias is a form of confounding that occurs when a drug is preferentially prescribed to patients with different baseline characteristics. Standardized differences will be applied when assessing channeling bias.

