## **9. RESEARCH METHODS**

### **9.1 STUDY DESIGN**

This observational multi-centre and cross-sectional study will be conducted in cardiology departments, in at least 102 centres in Spain.

The design of the study impose an only visit to be performed that will coincide with one of those performed by the patients as part of routine follow-up of their disease, without interfering with usual clinical practice of the investigator.

A specific therapeutic strategy has already been assigned to each included patient, based on routine practice and without interference with the physician's prescription habits. The observational nature of the study is ensured as no diagnostic or therapeutic intervention outside of routine clinical practice will be applied.

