## **9.2 SETTING**

Approximately 1.000 patients with NVAF currently on NOAC treatment and having initiated their first NOAC starting from November 2016 (Health Authorities positioning report publication) are planned to be included in the study. To minimize selection bias at the patient level, 10 consecutive patients from each site who meet entry criteria will be enrolled.

It is necessary to ensure that study population is representative of the entire national territory. Therefore, patients will be recruited from Hospitals (different levels of medical care: primary hospital, secondary hospital) in different geographical areas according to the distribution of the overall population in this area. Site selection will be performed in order to secure representativeness of the NVAF population treated with NOACs.

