### **9.2.3 Study visits**

The design of the study imposes a single visit to be performed that will coincide with one of those performed by the patients as part of routine follow-up of their disease, without interfering with usual clinical practice of the investigator. After signing the informed consent

(if patient agreed to participate in the study) patients will be asked to answer the questions necessary to evaluate the patient's knowledge about anticoagulant treatment at the unique study visit. Other variables needed to address study objectives will be obtained directly from patient medical records. The end of the single study visit is the end of the study for each patient.

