#### **9.3.2 Outcomes**

##### **9.3.2.1 Primary outcomes**

The primary outcome is the usage of NOACs, in patients with NVAF, in the hospital setting, based on the baseline characteristics at the time of first NOAC initiation. Baseline (at time of first NOAC initiation) variables will be analysed descriptively by NOAC type. Treatment groups will be defined according to first NOAC prescribed. The time frame for assessing this outcome is 7 months (recruitment period).

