9.2. NOAC TREATMENT MANAGEMENT

A description of the first prescribed NOAC and other NOACs (if applicable) will be made, indicating:

- ✓ Number and percentage of patients according to NOAC type and dose
- ✓ Time in treatment calculated as the difference between start date and end date, if both are available and in other case informed consent date will be used (time to beginning study); it will be described as quantitative variable.
- ✓ NOAC Dose; it will be described as qualitative variable.
- ✓ Number and percentage of patients who need discontinue treatment or dose adjustment or change a new NOAC; in this case, reason for change.
- ✓ Number and percentage of patients who change other NOAC, including type of new NOAC or new doses, time in treatment if start and end dates, and time after first NOAC.

On the other hand, frequency of visits to the physician will be assessed quantitatively and qualitatively.

A descriptive analysis of the history of thromboembolic and hemorrhagic events presented by the patients will be carried out. First, the number and percentage of patients with or without thromboembolic and hemorrhagic events would be provided. A description will be made of the type of event suffered, if it was related to NOAC and as well as the number of times, for the following two types of events:

Thromboembolic events:

- TIA
- Ischaemic stroke
- Haemorrhagic stroke
- Embolism systemic
- Deep vein thrombosis
- Pulmonary embolism
- Stable angina
- Unstable angina
- Myocardial infarction without ST segment elevation
- Myocardial infarction with ST segment elevation

Bleeding events:

- Intracranial
- Digestive
- Genitourinary
- Gingival
- Nasal
- Pulmonary
- Articular-muscular
- Conjunctival
- Other

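### Patients are enrolled at routine cardiology visits, so the unweighted summary of visit frequency in SAP 9.2 is biased upward; a weighted sensitivity summary beside it would show the plausible range

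*Protocol*

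**What the plan says.** Protocol 9.1 places the study in hospital cardiology: it "will be conducted in cardiology departments, in at least 102 centres in Spain". Protocol 9.2.3 describes a "single visit to be performed that will coincide with one of those performed by the patients as part of routine follow-up of their disease". Within a site the rule in Protocol 9.2 is that "10 consecutive patients from each site who meet entry criteria will be enrolled". Protocol 9.3.2.1 gives a recruitment period of seven months, which matches the milestone dates of November 2017 to May 2018.

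Protocol 9.9 lists the resulting selection among its limitations. It says "Patients seen by their physician less than twice per year are therefore less likely to be included in the study", and then "Patients with higher frequency of visits are more likely to be included in the study and could be over-represented in the sample".

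Visit frequency is also an outcome. Protocol 9.3.2.2 lists it under NOAC treatment management, and Table 9.3.2.2:1 shows it as an interview question: "How many times a year do you visit the cardiologist". For its analysis, SAP 9.2 says that "frequency of visits to the physician will be assessed quantitatively and qualitatively". SAP 5 adds that secondary outcomes are described for the total sample and that patients with a missing value are left out of that outcome's analysis. Neither document plans weights, a sensitivity analysis or a caveat for this item.

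**The concern.** The variable that drives selection is the variable being reported. Someone seen four times a year has more chances to be the next eligible attender than someone seen once. Enrolling attenders in sequence stops the investigator from choosing among them, but it does not equalise those chances.

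The raw mean, and the raw share of frequent attenders, therefore describe the people found in clinic on a given day. They do not describe the NOAC patients whom the clinic looks after. A reader of the report would probably take the figure in the second sense, as Protocol 9.2 aims for a sample representative of the NVAF population treated with NOACs. The limitation in Protocol 9.9 is general. It is not tied to this outcome and is not carried into the SAP.

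**Working it through.** **Plan's own figures.** The documents give no figure for visit frequency. The only precision figures are the 95% interval widths in Protocol Table 9.5:1, for 1,000 patients: 3.73, 4.95, 5.67, 6.06 and 6.18 points at 10 to 50%. Wilson score intervals give 3.72, 4.95, 5.67, 6.06 and 6.19, so the table reproduces to within 0.01 point. It covers random error only.

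**Direction.** Let V be visits per year, with population mean μ and variance σ². Let π(V) be the chance of inclusion.
- The unweighted sample mean estimates E[Vπ(V)]/E[π(V)]. This exceeds μ whenever π rises with V and V varies.
- If π is proportional to V, it equals E[V²]/E[V] = μ + σ²/μ.
- The mean weighted by 1/V estimates E[π(V)]/E[π(V)/V]. It equals μ if π is proportional to V, and is at or below μ if π rises more slowly than that.
- So if π rises with V, but no faster than proportionally, the two means bracket μ. The same holds for the share of patients above any cut-off of V.

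**Example (assumed distribution).** 40/35/15/10% of patients make 1/2/3/4 visits per year.
- μ = 0.40 + 0.70 + 0.45 + 0.40 = 1.95.
- E[V²] = 0.40 + 1.40 + 1.35 + 1.60 = 4.75.
- True share with 3 or more visits: 25%.

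Three inclusion models:
1. *Proportional* (sites fill their ten places quickly). Unweighted mean 4.75/1.95 = 2.44, or +25%. Unweighted share with 3 or more: (0.45 + 0.40)/1.95 = 43.6%. The weighted mean is 1.95.
2. *Every attender over seven months, evenly spaced visits*, π = min(1, 7V/12), which is 0.583, 1, 1, 1. Unweighted mean 1.783/0.833 = 2.14, or +10%. Weighted mean 0.833/0.483 = 1.72, or −12%. Share with 3 or more: 30% unweighted, 15.5% weighted.
3. *Every attender over seven months, random visits*, π = 1 − exp(−7V/12), which is 0.442, 0.689, 0.826, 0.903. Unweighted mean 1.392/0.632 = 2.20, or +13%. Weighted mean 0.632/0.361 = 1.75, or −10%. Share with 3 or more: 34% unweighted, 18% weighted.

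The error in the unweighted share is thus about 5 to 19 points. The largest half-width implied by Table 9.5:1 is 6.18/2 = 3.09 points.

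**Cost in precision.** In model 1 the sample mean of 1/V is 1/1.95 = 0.513. The sample mean of 1/V² is (0.40 + 0.175 + 0.05 + 0.025)/1.95 = 0.333. The design effect is 0.333/0.513² = 1.27, so the effective sample size is about 79% of the actual one.

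**Sensitivity to the assumed distribution.**
- Narrower spread, 30/40/20/10% at 1/2/3/4 visits: true mean 2.10; unweighted 2.52 (+20%) in model 1 and 2.26 to 2.32 (+7% to +11%) in models 2 and 3.
- Wider spread, 40/25/10/10/10/5% at 1/2/3/4/6/12 visits: true mean 2.80; unweighted 5.25 (+87%) in model 1 and 3.16 to 3.46 (+13% to +23%) in models 2 and 3.

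The direction is upward in every case.

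**The case against.** The strongest reply has three parts.

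*The protocol already says this.* Protocol 9.9 names the mechanism and its direction, and also admits other gaps in representativeness. That is true, and a reader should not infer that the bias was hidden. What is missing is the link to the one outcome that is itself the selection variable, and any handling in the SAP.

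*Weighting can do as much harm as good.* A reader might infer that the 1/V-weighted figure is the right answer and should replace the raw one. The documents do not support that. They do not say how fast a site fills its ten places. If sites enrol over the full seven months, the weights over-correct by about as much as the raw mean over-states: in model 2, −12% against +10%. This part of the objection stands in full and determines the form of the fix. The weight is also an answer about visits to the cardiologist, not a count of attendances at the recruiting clinic, and it is undefined for an answer of zero.

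*It is one descriptive item in a study without hypothesis tests.* This also stands. It limits the importance of the point, not its correctness.

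**Conclusion.** The point holds as a narrow one. The unweighted visit-frequency summary is biased upward as an estimate for NOAC patients attending these departments, and neither document connects the acknowledged selection to that result. The direction needs only that inclusion rises with visit rate, which Protocol 9.9 accepts, and that visit rates vary. The size cannot be derived from the documents. In the main example it is +10% to +25%, and across the distributions tried it is +7% to +87%, all on assumed figures.

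A reader might go further and infer that every characteristic correlated with visit frequency, including the three primary variables, is shifted upward too. That does not follow. The direction depends on the sign of each correlation, and the documents report none.

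**What to change.** A cheap improvement to SAP 9.2:
- Keep the unweighted summary and state beside it that it is biased upward because patients are enrolled at visits.
- Add a sensitivity summary weighted by 1/(reported visits per year), and present the two as a range. Say that they bracket the true mean if inclusion rises with visit rate no faster than proportionally, and that 1/V weights over-correct when a site enrols over many months.
- Where each site's enrolment duration is available, weights built on it may be used instead.
- State a rule for answers of zero and for missing answers. SAP 5 already drops missing values from an outcome's own analysis, but a weighted run of any other variable needs its own rule.
- Repeating age, CHA₂DS₂-VASc and HAS-BLED with the same weights is optional, and a sensitivity analysis only.

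The cost is a few lines of SAP text and one weighted run; the variable is already collected. Three downsides should be stated. The weight is self-reported. Effective sample size falls, to about 79% in the example. Weighting also does not correct for the fixed ten patients per site, for patients treated in other settings, or for those who stopped NOAC treatment early.

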### **9.2.1 Study sites**

Cardiology departments, in a hospital setting, who regularly prescribe NOACs for stroke prevention in NVAF patients, will be selected to participate. The study will be performed among all the national territory. Site feasibility assessments will be performed by the CRO during the process of site selection.

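### Protocol 9.2 requires a sample representative of NOAC-treated NVAF patients, but a fixed 10 per site with unweighted summaries weights every site equally, and the larger-hospital shortfall conceded in 9.9 is neither measured nor corrected

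*Protocol*

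**What the plan says.** Protocol 9.2 sets the aim: "It is necessary to ensure that study population is representative of the entire national territory". It adds: "Site selection will be performed in order to secure representativeness of the NVAF population treated with NOACs". Two design measures support this. Hospitals of different care levels are to be included, and recruitment is spread "in different geographical areas according to the distribution of the overall population in this area".

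The intake rule in the same section is a flat quota: "10 consecutive patients from each site who meet entry criteria will be enrolled". Protocol 9.1 plans the study "in at least 102 centres in Spain", and 9.5 gives a total of approximately 1000 patients.

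Protocol 9.9 then states the effect of the quota: "having 10 patients recruited in each site, patients from the larger practice hospitals will also be under-represented".

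The planned analysis (Protocol 9.7 and 9.7.1; SAP 5, 8 and 9) consists of frequencies, percentages, means, medians and standardized differences. No weights are mentioned. SAP 6 lists patient counts by centre, autonomous community, and NOAC type and dose, but not by hospital level. Summaries by factors of interest are promised without the factors being listed. On site selection, Protocol 9.2.1 says: "Site feasibility assessments will be performed by the CRO during the process of site selection". It does not say what those assessments record.

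**The concern.** The target population named in 9.2 is patients, not hospitals. With the same number taken from every site, a patient at a high-volume hospital has a smaller chance of selection than one at a low-volume hospital. An unweighted percentage then averages over sites rather than over patients. If choice of NOAC, patient profile or reason for initiation varies with hospital size, the two averages differ, and the precision table in Protocol 9.5 does not cover that difference because it reflects random error only.

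Protocol 9.9 lists several selection problems. Patients treated outside cardiology, or who stopped their NOAC before enrolment, cannot be recovered from the sample. Unequal sampling fractions between sites are different: they can be examined if site volume is known. The plan does not collect it, so a bias that the protocol itself expects would go unmeasured in a study meant to describe anticoagulation management in Spain.

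**Working it through.** **1. The plan's own figures.** Protocol Table 9.5:1 gives full 95% CI widths at n = 1000 of 3.73, 4.95, 5.67, 6.06 and 6.18 points for prevalences of 10, 20, 30, 40 and 50%. The Wald width 2 × 1.96 × √(p(1−p)/n) gives 3.72, 4.96, 5.68, 6.07 and 6.20. The Wilson interval gives 3.72, 4.95, 5.67, 6.06 and 6.19. The table reproduces under simple random sampling. At 30% the half-width is 5.67/2 = 2.8 points. Sites × quota = 102 × 10 = 1020, consistent with approximately 1000.

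**2. Implied weights.** Each site that fills its quota carries 10/1020 = 0.98% of the sample. With full quotas and no missing data, the pooled proportion is the simple mean of the site proportions.

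**3. Gap between the equal-weight and patient-weighted proportions.** Hospital volumes and differences between hospitals are not in the documents. Assumptions: 30 of 102 centres are large, each with k times the eligible patients of the others, and a NOAC has a share of 25% in the other centres and 25% + d in the large ones.

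- Sample share of large centres: 30/102 = 29.4%.
- Patient share of large centres: 30k/(30k + 72). For k = 3, 90/162 = 55.6%. For k = 5, 150/222 = 67.6%.
- Error = (sample share − patient share) × d.

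| d (points) | k = 3 | k = 5 |
|---|---|---|
| 0 | 0 | 0 |
| 5 | −1.3 | −1.9 |
| 10 | −2.6 | −3.8 |

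In full for d = 10:
- Unweighted: (30 × 0.35 + 72 × 0.25)/102 = 27.9%.
- Patient-weighted, k = 3: (90 × 0.35 + 72 × 0.25)/162 = 30.6%.
- Patient-weighted, k = 5: (150 × 0.35 + 72 × 0.25)/222 = 31.8%.

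The error is linear in d, so a larger assumed difference gives a larger error. For example, with 25% of hospitals large, k = 5 and d = 20, it is (0.25 − 0.625) × 20 = −7.5 points.

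**4. Cost of weighting under the same assumptions.** Kish factor = (patient share)²/(sample share), summed over the two groups of centres.

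- k = 3: 0.556²/0.294 + 0.444²/0.706 = 1.33; effective n = 1020/1.33 ≈ 770.
- k = 5: 0.676²/0.294 + 0.324²/0.706 = 1.70; effective n = 1020/1.70 = 600.
- Half-widths, ignoring clustering: 1.96 × √(0.306 × 0.694/770) ≈ 3.3 points and 1.96 × √(0.318 × 0.682/600) ≈ 3.7 points.

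**5. When weighting lowers total error.** At 30% prevalence the unweighted variance is 0.21/1020. Weighting reduces mean squared error once bias² exceeds (Kish − 1) × 0.21/1020. That is a bias above √(0.33 × 0.21/1020) = 0.8 points for k = 3, or √(0.70 × 0.21/1020) = 1.2 points for k = 5, again ignoring clustering.

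**The case against.** The best defence is disclosure. Protocol 9.9 states this limitation and several related ones, so a careful reader is not misled. That stands: nothing is hidden, and no figure in the plan is wrong because of it. It does not reconcile 9.9 with the requirement in 9.2, or supply a way to see how much the imbalance matters.

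Three stronger readings are tempting, and the documents do not support them.

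- A reader might infer that 9.2 claims representativeness has been achieved. It states an aim of site selection, backed by spread over hospital levels and regions. Those measures do not adjust for hospital volume, but they are not nothing.
- A reader might infer that the results simply describe the average Spanish hospital. That would require site selection to be unrelated to volume. Sites must prescribe NOACs regularly, and selection in proportion to volume would make an equal take self-weighting. No such scheme is described, however, and 9.9 says some under-representation remains.
- A reader might infer that the error is known to exceed the stated precision. It is not. With a 5-point difference it stays inside the 2.8-point half-width; with no difference it is zero.

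It is also fair that the worked example concerns NOAC share, whereas the primary variables are age, CHA2DS2-VASc and HAS-BLED by first NOAC. No size has been shown for those, for the standardized differences or for appropriateness. Finally, weighting sites that were not drawn by probability sampling does not yield a national estimate. These points limit what the remedy can deliver; they do not remove the case for a supplementary analysis.

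**Conclusion.** The point holds as a gap between aim and analysis. Protocol 9.2 requires representativeness of a patient population, the quota gives sites equal weight, 9.9 concedes the direction of the imbalance, and neither document plans to measure or correct it. The size is not derivable from the documents. With 30 of 102 centres large, volume ratios of 3 to 5 and prescribing differences of 0 to 10 points, all assumed, the error in a NOAC share is 0 to about 3.8 points against a half-width of about 2.8. Confidence in that magnitude is low; confidence that the plan cannot tell which end of the range applies is high. This is a cheap improvement, not an error that invalidates the planned analysis.

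**What to change.** 1. Record each site's approximate number of eligible NVAF patients on NOACs at the feasibility assessment, unless already captured there. Put the same question to sites already selected.
2. Keep the unweighted analysis as primary. In SAP 5, add a volume-weighted sensitivity estimate with site-clustered 95% intervals for age, CHA2DS2-VASc, HAS-BLED, NOAC shares and appropriateness, shown beside the unweighted figures.
3. Add a descriptive split by hospital level, which 9.2 already uses as a sampling dimension, and name it among the factors of interest.
4. Reword Protocol 9.2 so that its aim agrees with 9.9, and limit conclusions to the participating cardiology departments.

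The cost is one question per site, a few lines in the Protocol and SAP, and one additional run. The SAP methods currently specify no confidence intervals, so the clustered intervals are an addition. The downsides are approximate volumes and an effective sample of roughly 600 to 770 of 1020 for the weighted estimates under the assumptions above. Weighting also corrects only the unequal take among selected sites; it leaves site selection, visit frequency and early discontinuation untouched.
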